All SMS messages and e-mails will comply with security procedures according to NIH Human Protection Subject Guidelines [47]. The PI will be responsible for monitoring of adverse events and data quality and safety, as this is a low-risk investigation. The Plan for monitoring of data quality and accuracy will include the following: Data entry from the CRT will be done through specific software that will include range and inter-item consistency checks. Entries out of the expected range will not be permitted. Re-entry of 20% of questionnaires will be done for quality control. The data cleaning process will actively search for errors in a planned way.

SPECIFIC AIM 2: To evaluate the implementation strategy and identify barriers and facilitators to implementation of the multi-component mHealth intervention.

RE-AIM and CFIR frameworks will guide the implementation evaluation: as illustrated in Figure 5. The CFIR comprises 39 common constructs from published implementation frameworks and models and organizes them into five major domains.⁴⁵ In this study we will analyze the following domains:

Intervention Characteristic (Relative advantage; adaptability; complexity and cost); **Outer Setting** (Patient needs and resources; external policies and incentives); **Inner Setting** (Structural characteristics; tension for change, relative priority and available resources; access to knowledge and information); and **Characteristics of Individuals** (Knowledge and beliefs about the intervention; perceived self-efficacy).⁴⁵ Proposed quantitative and qualitative measures based on RE-AIM and CFIR frameworks are presented in Table 1.

[figure not shown]

Figure 5. Implementation evaluation. Adapted from Damshroder et al., 2015.⁶⁴

We will use data from the RCT database and will also conduct a self-administered semi-structured survey of CHWs, semi-structured interviews with key stakeholders, and a survey of HPV+ women. The CFIR will be used to develop surveys and interview guides and guide data collection and analysis. Eight weeks after the RCT (intervention and measurement of primary outcome) is finished we will hold a workshop as a closing activity to present preliminary results to CHWs and health authorities. During this workshop, CHWs will be asked to complete an anonymous, **self-administered semi-structured survey** to evaluate their perspectives and acceptability of the intervention (see outcomes and qualitative evaluation in Table 1), and about barriers and facilitators of the intervention, considering a subgroup of CFIR constructs. We will administer the survey during the closing activity to assure a high level of response. Project staff members will emphasize that participation in the survey is anonymous and voluntary; all participating CHWs will sign consent forms. Those CHWs who were not able to attend this closing activity will receive the survey by mail and will be requested to send it to project staff in a blind envelope. A specific database built for the Survey will be used for analysis, which is described in the **Quantitative data analysis Section**.

Qualitative data from open-ended questions will be transcribed, coded, and analyzed as described in the Qualitative data analysis Section.

In the third year of the project, we will conduct **Semi-structured interviews with stakeholders** to evaluate their acceptability of the intervention and perspectives on how to build and enhance project sustainability (See qualitative evaluation in Table 1). Stakeholder participants will include leaders and intermediate coordinators of PHC, HPV laboratory, and Women Health Department, the director of the provincial Program on Cervical Cancer Prevention, Minister and Secretaries of Health, and heads of gynecology services. In semi-structured interviews, “the interviewee has the possibility to talk freely about the issue in question without being held to the question asked”.⁶⁵ Constructs to be considered in the script will include: Relative Advantage, Adaptability, Complexity and cost; Patient Needs and Resources, and External Policies and Incentives; Structural Characteristics; Tension for Change; Relative Priority; . These constructs will be measured at 8 weeks after the end of the trial period (implementation of the intervention + measurement of primary outcome). Interviews with health authorities will be carried out also include questions to evaluate the potential for programmatic incorporation of the multicomponent mHealth Intervention, as to measure the Maintenance dimension of RE-AIM. The sample size will be determined based on relevance and theoretical saturation.⁶⁵ We will select participants to ensure a wide range of responses are captured (i.e., we expect stakeholder with different interests, backgrounds, and involvement/interaction with intervention activities to have varied opinions) and to allow comparisons between them. To ensure we include enough stakeholders from relevant groups in the sample, we plan to conduct at least 20 interviews; however, we will recruit until we reach theoretical saturation and no longer find anything new about relevant dimensions, though this can depend on the complexity of the dimensions being analyzed.⁶⁶ Qualitative data will be recorded, transcribed, coded, and analyzed as described below (Section on Qualitative data analysis).

Finally, we will carry out a **Structured questionnaire among HPV+ women (Women Survey)** to evaluate their acceptability of the strategy, their perspectives about the implementation, and reasons for adherence and non-adherence to triage. We will survey all HPV+ women from the RCT intervention group (approximately 240 women), 5 months after the HPV test result (this is, one month after measurement of the primary outcome), irrespective of their triage status. The questionnaire will include open and closed questions with dimensions related with women's experiences and

Table 1. Measurements and data sources proposed for Implementation Evaluation based on RE-AIM and CFIR

	Quantitative outcomes	Qualitative evaluation	Data source
Reach Representativeness of women reached by the intervention (quantitative data)	-% of eligible women who accepted to participate in the study -Socio-demographic information of participant/non-participant women		RTC database (Trial Form)
Effectiveness in increasing women's adherence to triage (quantitative and qualitative data)	-Primary outcome: percentage of women with triage smears 120 days after test results are registered in SITAM.	Reasons for adherence/non adherence to triage.	RCT database (SITAM) HPV+ Women Survey
Adoption by CHWs of the strategy of visiting HPV+ women after receiving SMS messages and e-mails*	-% of CHWs that visited at least one HPV+ women after receiving the SMS message and e-mail.		RCT database (Trial Form+Automated System Monitoring Registry)
Acceptability of the intervention by adopters	-% of CHWs that agreed with programmatic incorporation of the mHealth intervention.	CFIR construct: Knowledge and beliefs about the intervention; perceived self-efficacy	Self-administered semi-structured survey of CHWs
Implementation of intervention activities according to protocol (quantitative data)	-% of randomized CHWs that participated in trainings. -% of SMS messages that reached a valid phone number. -% of HPV+ women who sent confirmatory SMS messages. -% of e-mails that reached a valid e-mail address. -% of CHWs who sent confirmatory e-mails.		Automated System Monitoring Registry and Training Attendance List
Acceptability of the intervention by women. (quantitative and qualitative data)	-% of women who accept and are satisfied with the intervention.	Women level Experience and perception of the intervention; acceptability of SMS messages, pertinence of frequency, reception time and content of SMS messages.	HPV+ Women Survey
Barriers and facilitators to implementing and administering the intervention (qualitative data)		Stakeholder/CHWs level CFIR constructs: Relative Advantage; Adaptability; complexity and cost. Patient Needs & Resources and External Policies & Incentives. Structural Characteristics; Tension for Change; Relative Priority and available Resources, Access to Knowledge & Information.	Semi-structured interviews with stakeholders and Self-administered semi-structured survey of CHWs
Maintenance		Intention to incorporate the strategy.	Interview with Stakeholders

*Adoption of the Automated System will not be measured as it will be a unique centralized system linked to SITAM

perceptions, including acceptability and relevance of SMS message frequency, receipt time, and content; perceived effect of the multiple components of the intervention on their adherence, and reasons for adhering/not adhering to triage. The nominated list of these women and their contact details will be extracted from the RCT database. Trained interviewers will contact these women via telephone to make an appointment to visit them at their homes to administer the questionnaire. The training will be carried out by the project staff; it will include formal aspects regarding applying the questionnaire as well as skills for developing a connection with the interviewees. Interviewers will be provided with a list of women to interview with contact information.

Quantitative data analysis. This section refers to the analysis of data from the Women Survey and the Self-administered semi-structured survey of CHWs. A descriptive analysis of each study dimension will be carried out using simple frequencies and percentages for each of the variables under study. The association between the variables will be measured using the Chi square test of independence. Outcomes will be summarized as percentages and compared across women/CHWs socio-demographic characteristics using logistic regression. Results will be presented as estimates and 95% confidence intervals. Analysis will be conducted using STATA (version 13.0) and/or SAS (version 9.3).

Qualitative data analysis. We will use CFIR as an organizing and analytic framework for Aim 2. We will use an iterative approach to analyzing qualitative data, developing an initial codebook after reading the transcripts and responses and adding or revising thematic codes as they emerge from the data.⁶⁷ To ensure coding reliability, two researchers will independently code and perform consistency checks. They will hold regular discussions to resolve disagreements and reach consensus and will discuss uncertainties with a third team member. After coding, thematic and content analysis will be conducted. Content analysis methodology,⁶⁸ is defined as “a set of communication analysis techniques aimed at obtaining indicators that permit the inference of knowledge relative to the conditions of production/reception of messages, through a systematic and objective description of the message content”.⁶⁸ We will use Atlas.ti to organize, analyze, and summarize data, generating a compilation sheet of the findings. Data from qualitative studies will be translated into English, for team work with the two co-investigators from the Dana-Farber Cancer Institute. Key documents will be back-translated.

STAKEHOLDER ENGAGEMENT TO CHANGE AND READINESS FOR CHANGE. Argentina has become a pioneer in the introduction of new technologies for HPV-based cervical cancer prevention. In 2011 the National Ministry of Health approved the incorporation of the test as a nation-wide screening method and between 2012-2014 the Jujuy Demonstration Project was carried out to implement and evaluate the programmatic components of an HPV-based screening strategy.¹¹ The province health authorities and professionals, actively participated in the design, implementation and evaluation of this project. They were also actively engaged in the above mentioned EMA project.¹⁴ As a result of this, incorporation of HPV-self collection offered by CHWs began in 2014 as a programmatic, routine strategy. The need for a mHealth intervention to increase triage of HPV+ women was brought up by Jujuy health authorities in view of the low percentage (30%) of these women who have undergone cytology within 120 days since initial screening.⁷ In addition, the Jujuy Minister of Health, [name], has given high support to this project, as increasing adherence to triage is a high priority programmatic goal (see letter of support). This shows a real engagement of stakeholders for adoption and rolling out of the intervention if its effectiveness is confirmed.

DISSEMINATION PLAN. We will carry out active dialogue and meetings with health authorities at several moments of the project to present preliminary results and discuss implementation issues and future scaling-up. We will produce a video about the process of the intervention, with voices of women, CHWs and health authorities. Video producers will contact selected women, CHWs and health authorities after field work is finished. We also expect to publish at least three papers in high

impact international journals, and present results in several congresses including the Annual Conference on the Science of Implementation and Dissemination. Also, we will carry out several meetings with health authorities and heads of services to plan other dissemination activities in a participatory manner. Communication channels of the cervical cancer prevention programs (Twitter, Facebook, websites, meetings) will also be used to disseminate results.

FEASIBILITY OF THIS STUDY: The proposed study is led by the Center for the Study of State and Society, in association with Harvard University from the United States, and Deakin University from Australia, with support from the Argentinean National Cancer Institute and the Jujuy Ministry of Health. The need for a mHealth intervention to increase triage of HPV+ women was brought up by Jujuy health authorities in view of the low percentage of these women who have undergone cytology. The Head of the provincial cervical cancer prevention program has contributed to the study design. The Jujuy Province Ministry of Health has provided full support to the proposed project, as well as the Provincial Program on Cervical Cancer Prevention and the Director of the National Cancer Institute from Argentina, [name].

IMPACT AND FUTURE DIRECTIONS. Together, the results of both aims of this project will generate rich information on the effectiveness of a mHealth intervention on cervical cancer triage, the acceptability of mHealth interventions and CHW counseling, and the barriers and facilitators to implementing a multi-component intervention. These combined results will provide powerful evidence to scale-up a comprehensive multi-component mHealth intervention to the Argentina Ministry of Health that may have wide applicability in the Region, other LMICs, and even Latina populations in the US.

References:

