(see Analysis Plan below). In addition, a larger number of CHWs in the intervention group will benefit the assessment of the implementation outcomes. Based on PHC records and previous experience¹⁴ we estimate that each CHW will enroll an average of 20 eligible women in a 10-month period. We assumed an attrition rate of 20% due to problems with mobile phones (i.e. non-identified number, unpaid phone bill, lack of signal, etc.), SMS messages not delivered and/or other issues. Under a 13% prevalence of HPV+ in this population,¹¹ we estimate that each CWH will contribute with an average of 2 HPV+ women. **Primary outcome:** The target sample size (120 CHWs in the MH group and 80 CHWs in the UC group, each one providing 2 HPV+ women) will have 97% power to detect a 20% triage difference between the two groups when the control group has a 30% triage in a 120-days period (two-sided test, alpha=0.05). Correlation induced by the CHWs was included in power calculations assuming an intra-class correlation coefficient of 0.10. **Secondary outcome:** Under the same assumptions, the proposed sample size will have 90% power to detect a difference of 10% in triage between groups when the control group has a 15% triage by day 60.

A specifically built database will be used (RCT database), combining information from the Trial Form, the AS Monitoring Registry, and SITAM, the national screening information system.⁵² The Trial Form will register information about the randomization group, agreement to participate in the study, women's socio-demographic data, and tasks performed by the CHWs (contact after reminder and reasons of no contact). Data on HPV testing, triage, diagnosis and treatment will be uploaded importing data from SITAM, linking the records through each woman's national identification number. The AS Monitoring Registry will include data from the Automated System regarding receipt of confirmatory SMS messages and e-mails, and valid phone numbers and e-mails. Data entry will be done through specific software that will include range and inter-item consistency checks. Data will be stored in files compatible for analysis with statistical packages (Stata).

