Analysis plan: All analysis will be conducted on an intention-to-treat (ITT) basis; the effect of the multi-component mHealth intervention on the primary outcome will be assessed using a generalized estimating equations approach. The model (logit link, and binomial distribution) will include trial group as fixed effect and CHWs as the clustering variable. Potential effect modification due to rural/urban location of the woman and CHW gender will be evaluated. Baseline socio-demographic characteristics of the women will be compared between groups using the same model with link and distribution selected depending on the variable. Factors showing clear unbalance between arms will be included in the model proposed above to adjust for potential confounding. The same approach will be used to estimate the intervention effect on the secondary outcome. Analyses will be conducted using STATA 14.0 or SAS v.9.4. The trial will follow the CONSORT extension for cluster randomized trials reporting guidelines.⁶³

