Potential problems and limitations: One of the potential limitations of randomization of CHWs is the **risk for contamination** due to CHWs assigned to different study groups, but working in neighboring areas, which could activate CHWs and women in the UC group. However, our prior work using CHW cluster randomization¹⁴ suggests that this risk is low and the effect of contamination is minimal. If such effect occurs, we expect them to be moderate because meaningful improvements in adherence to triage require a systematic effort to address problems related to follow-up adherence which are unlikely to occur in the absence of a specific intervention. Also, **it is not possible to blind CHWs (clusters) or women in this study.** However, laboratory personnel processing the HPV-test and personnel entering data in SITAM, the national screening information system, will be blind. Moreover, the assessment of primary and secondary outcomes will be objective, as data on triage is extracted from SITAM. Nevertheless we will compare demographics characteristics and screening history of women enrolled in the two study groups and will control in the analysis for any variable showing unbalance between study groups. Other problems that might affect the RCT are those related to **poor cell phone network coverage or reception or gaps in service due to unpaid telephone bills.** However, the sample size calculations accounted for this type of attrition, as described above. Finally, **if women do not confirm their identity within one week of initial SMS**

message reception, it will affect the delivery of the intervention (number of SMS messages the woman will receive). To minimize this potential problem, CHWs will emphasize the importance and ease of confirming identity as soon as possible, ideally within 24 hours, not exceeding 7 days.

We **evaluated and ruled out alternative designs** such as having a three group trial (comparing SMS messages to women vs. SMS messages to women + SMS message and e-mail to CHWs vs. UC) because the main aim of the trial is to assess the effect of the multi-component intervention, not each component separately. In addition, such a trial should include a larger number of CHWs, which would attempt against feasibility of a study that will take place in a real-world, programmatic context. Instead, we propose a time series approach to explore the differential impact of each component of the intervention.

Safety and monitoring

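### Undelivered SMS is taken out of the sample size as 20% attrition, although under ITT with SITAM outcomes these women stay in the analysis; n and both power figures need restating, but the primary outcome is not underpowered on this ground

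*Combined protocol and SAP*

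**What the plan says.** The section on randomization and sample size expects each CHW to enrol 20 eligible women, with 13% HPV+. It then says "We assumed an attrition rate of 20% due to problems with mobile phones", and lists undelivered SMS and other issues under the same allowance. It arrives at an average of 2 HPV+ women per CHW. The target sample is given as "120 CHWs in the MH group and 80 CHWs in the UC group, each one providing 2 HPV+ women". For a usual-care rate of 30% by day 120, an intra-class correlation of 0.10 and a two-sided 5% level, the plan's claim is that this sample "will have 97% power to detect a 20% triage difference between the two groups". For the day-60 outcome it claims 90% power for 10 points above a control rate of 15%, under the same assumptions.

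The analysis plan says "All analysis will be conducted on an intention-to-treat (ITT) basis". Triage data come from SITAM, linked by national identification number. Under potential problems and limitations, poor coverage and unpaid bills are answered with the statement that "the sample size calculations accounted for this type of attrition, as described above".

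**The concern.** A dead number or a failed message does not remove a woman from the outcome. Her triage status is in SITAM whether or not she was reached, and ITT keeps her in the denominator. She is a non-receiver, and non-receipt acts on the size of the difference, not on the number analysed. The plan makes the allowance in n, and the limitations section treats the matter as closed on that basis.

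The loss is also applied to usual care, where no study SMS is sent and undelivered study messages cannot occur.

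At stake is whether the stated n and power describe the analysis that will be run. The question is sharper for the day-60 outcome. It is meant to isolate the SMS component and is measured before any CHW prompt, so non-delivery would dilute it directly.

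**Working it through.** **Inputs (from the sample size section).** 120 vs 80 CHWs; 20 women enrolled per CHW; 20% attrition; 13% HPV+; ICC 0.10; two-sided alpha 0.05; primary 30% vs 50%; day 60 15% vs 25%.

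**Method.** With m HPV+ women per CHW, the design effect is DE = 1 + (m − 1) × 0.10, and effective n per arm = CHWs × m / DE. Power = Φ[(d − 1.96 × SE₀) / SE₁], where d is the difference, SE₀ uses the pooled proportion and SE₁ the two separate proportions. Cluster sizes are taken as equal.

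**Where the 2 comes from.** 20 × 0.80 × 0.13 = 2.08. Without the 20% loss, 20 × 0.13 = 2.6.

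**The plan's primary figure.** m = 2: DE = 1.10; effective n = 160/1.10 = 145.5 and 240/1.10 = 218.2. SE₀ = 0.0528 and SE₁ = 0.0509. (0.20 − 1.96 × 0.0528)/0.0509 = 1.90, so power is 97.1%. The stated 97% reproduces.

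**Primary outcome, all women kept.** If the whole 20% is non-delivery, m = 2.6 gives 120 × 2.6 = 312 and 80 × 2.6 = 208 women, 520 instead of 400. DE = 1.16; effective n = 269.0 and 179.3.

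| Share of benefit lost by the unreached 20% | ITT difference | Power |
|---|---|---|
| None, or 20 points is already the ITT difference | 20 points (50% vs 30%) | 99.0% |
| Half | 20 × (1 − 0.2 × 0.5) = 18 points | 97.1% |
| All | 20 × (1 − 0.2) = 16 points | 93.0% |

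If cluster sizes vary as a Poisson count, the last row becomes about 91%. Keeping m = 2 and also diluting to 16 points gives 87.1%, but that counts non-delivery twice.

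**Day-60 outcome.**

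| m | Rates | Power |
|---|---|---|
| 2 (the plan's inputs) | 25% vs 15% | 64% |
| 2.6 | 25% vs 15% | 73% |
| 2.6, half dilution | 24% vs 15% | 65% |
| 2.6, full dilution | 23% vs 15% | 55% |

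The stated 90% does not reproduce on the plan's own inputs: 64% with the pooled standard error, 67% with the unpooled. Of the 35 points between 90% and 55%, 26 (90 − 64) are present before non-delivery is considered. Moving non-delivery from n to the effect takes 64% to between 55% and 65%.

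**The case against.** The strongest reply is that the two faults offset. The n is too small, which is conservative, and the effect may be too large. The corrected range of 93% to 99% straddles the stated 97%, and the middle case equals it. No design decision changes. This stands.

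It can also be said that 20 points is already the ITT contrast, since the power statement speaks of a difference between the two groups in a pragmatic trial. That is possible. The documents do not give its basis, and an undiluted effect is only an inference from non-delivery being handled solely as attrition. The 99% case must therefore stay in the range.

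The 16-point case is an extreme bound. It needs the whole 20% to be non-delivery, although the allowance includes other issues, so 2.6 is an upper limit. It needs every one of the weekly messages to fail for these women, all of whom gave a working number at entry. And it needs them to gain nothing from the day-60 CHW visit, which does not depend on the woman's phone.

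A reader might infer that unreached women will be dropped from the mHealth arm only, biasing the comparison towards the intervention. The documents do not support this. The ITT rule keeps these women, no section proposes to exclude them, and SMS reach and confirmation appear in Table 1 as implementation measures.

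A reader might also blame non-delivery for the whole day-60 shortfall. Most of it is arithmetic.

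**Conclusion.** The point holds as an inconsistency between the sample size and the analysis. Non-delivery is treated as loss of women, in both arms, when under ITT with registry outcomes it is non-receipt in one arm. The expected number of HPV+ women is up to about 520, not 400.

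The primary outcome is not underpowered on this ground: power is about 93% to 99%, and the stated 97% is right for its own inputs. This rests on equal cluster sizes, an ICC of 0.10, and the 20% being wholly non-delivery.

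The day-60 claim of 90% cannot stand. It is about 64% on the plan's inputs, 73% with all women kept, and 55% to 65% if non-delivery cuts the difference to 8 or 9 points.

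A minor related point: the limitations section says that "if women do not confirm their identity within one week of initial SMS" message, fewer messages will be delivered, but the mHealth group procedure describes weekly messages that stop only on a registered Pap result. Confirmatory messages are mentioned elsewhere, and the SMS timeline figures are not shown in the text available, so the step may be described there. No rate is given, so its effect cannot be sized.

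**What to change.** 1. In the sample size section, take non-delivery out of n. Use up to 2.6 HPV+ women per CHW (about 312 vs 208), less any part of the 20% that is real loss of outcome data, stated separately.
2. Say whether 20 points is the ITT difference. If it is not, put the non-delivery allowance in the effect size and give its assumption.
3. Restate primary power as a range: about 99% at 20 points, 97% at 18, 93% at 16 as the bound.
4. Recalculate the day-60 power and correct the 90%, separating the arithmetic correction from any dilution.
5. Reword the limitations section to match. Add to the analysis plan, as clarification of ITT, that women with undelivered or unconfirmed messages are analysed in their assigned arm.
6. Reconcile the procedures and limitations sections on identity confirmation, and update the Women Survey figure of about 240, which carries the same 2 per CHW.

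The cost is wording and a short recalculation, with no change to design or recruitment. The one real downside is a much lower stated power for the secondary outcome.
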